2.7.5 Vital signs

The analyses of vital signs (systolic/diastolic blood pressure, pulse rate, and weight) will include summary statistics of change from baseline over time separately for DBTE by treatment group.

Summaries will be provided at each time-point for subjects meeting the following defined categories:

- Change from baseline: ≥ 15 mmHg in diastolic blood pressure and/or ≥ 20 mmHg in systolic blood pressure and analyzed for systolic blood pressure (< 90 mmHg, > 180 mmHg) and diastolic blood pressure (< 50 mmHg, > 105 mmHg)
- Change from baseline in heart rate of ≥ 15 bpm (ie, an increase of at least 15 bpm) or heart rate > 120 bpm
- Change from baseline in heart rate of ≤ -15 bpm (ie, a decrease of at least 15 bpm) or heart rate < 50 bpm

2.7.6 Antibody Formation - Immunogenicity (IG) analysis set

The number and percentage of patients who are positive for anti-AMG334 antibodies at baseline (Visit 101, Day 1, pre-dose) and who develop anti-AMG 334 antibodies (binding and, if positive, neutralizing) will be tabulated by treatment group for randomized subjects during DBTE. The list of subjects with positive at any time will be provided. In addition, the number and percentage of subjects who develop anti-AMG 334 antibodies at any time post-dose (Visit 199, 203, 299, 301) will be tabulated by DBTE treatment group for the entire study.

The Immunogenicity prevalence set includes all patients in the Full analysis set with a determinant baseline IG sample **or** at least one determinant post-baseline IG sample.

The Immunogenicity incidence set includes all subjects in the Immunogenicity prevalence set with a determinant baseline IG sample **and** at least one determinant post-baseline IG sample.

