5.6 Study completion and discontinuation

5.6.1 Study completion and post-study treatment

A patient will be considered to have completed the Double-Blind Treatment Epoch when the patient has completed Visit 199 in the protocol. A patient will be considered to have completed the Open-Label Treatment Epoch when the patient has completed Visit 299 in the protocol. A patient will be considered to have completed the PTA-Open-Label Treatment Epoch when the patient has completed Visit 499 in the protocol.

Patients can stay in the Open-Label Treatment Epoch for 156 weeks (3 years), or until the study is early terminated by the sponsor. Patients may stay in the PTA-Open-Label Treatment Epoch as specified in [Section 3.1](#).

The study will be considered complete (End of Trial) when the last patient completes their last visit (i.e., LPLV) in the study.

The patient's completion status will be recorded on the appropriate Study Phase Completion eCRF pages.

For all patients not continuing on AMG 334, either in the Open-Label Treatment Epoch or commercially, outside the study (if locally available), a safety follow-up visit (visit 301) should be conducted 16 weeks after the last AMG 334A dose administration. The information to be collected at this follow up visit is outlined in [Table 6-1](#), and [Table 6-4](#).

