Serum Pregnancy	X					X			
Urine Pregnancy		X	X	X	X		X		
ECG	X		X	X		X			
Anti-AMG Antibodies			X			X	X		
eDiary Dispensing		S							
eDiary Return			S	S	S	S		Pt brings to each visit for use at site	
Clinical Outcomes (eDiary)		Daily (Migraine days, [REDACTED] duration, severity, rescue medication)							

Epoch	Screen	Baseline ³	Double-Blind Treatment ^{1,4}				Follow-Up ²	Notes
Visit	1	2	101	102	103	199	301	Follow up visit is 16 weeks after last dose of IMP (V103 / Wk 8), which is 12 weeks after last DBT visit (V199 / Wk 12).
Week	-6	-4	Day 1	4	8	12/PSD/TD	24/FU	
MPFID (eDiary)			Daily					
C-SSRS	X	X	X	X	X	X	X	Should also be performed at unscheduled visits.
Concomitant Medications	X	X	X	X	X	X	X	
Adverse Events ⁷			X	X	X	X	X	
Serious Adverse Events ⁷	X	X	X	X	X	X	X	
Study Drug Administration ⁸			X	X	X			
Contact IRT ⁹	X	X	X	X	X	X		
Screening Phase Completion Form	X							
Baseline Phase Completion Form		X						
Double Blind Phase Completion form						X		
Follow-Up Phase Completion Form							X	

1 – All study visit target dates are to be calculated from the Day 1 visit date, and all study procedures for a given visit should be completed in the same day.
 
2 – The Follow-Up Visit is required for all patients who either discontinue study drug early or complete the study in either the Double-Blind or Open-Label Treatment Epochs and do not continue commercial drug (if locally available).
 
3 – Enrollment into the Baseline Epoch can occur only if the patient successfully completes all requirements for the Screening Epoch.
								

Table 6-2 Assessment Schedule: Open-Label Treatment– Weeks 13-64 (1st year in Open-Label extension)

Epoch	Open-Label Treatment ^{1,2,3}													
	199	201	202	203	204	205	206	207	208	209	210	211	212	213
Visit														
Week	12	16	20	24	28	32	36	40	44	48	52	56	60	64
Open-label Treatment Phase Entry	X													
Complete Physical Exam	S													S
Brief Physical Exam		S	S	S	S	S	S	S	S	S	S	S	S	
Weight	X			X										X
Vital Signs ⁴	X	X	X	X	X	X	X	X	X	X	X	X	X	X
Chemistry/Hematology	X			X										X
Serum Pregnancy	X													X
Urine Pregnancy		X	X	X	X	X	X	X	X	X	X	X	X	
ECG	X	X												X
Anti-AMG Antibodies	X			X										X
eDiary Dispensing ⁵	S	S	S				S			S			S	
eDiary Return ⁵	S	S	S	S				S			S			S
Clinical Outcomes (eDiary) ⁶	Daily						X			X			X	
MPFID ^{6,9} (eDiary)	Daily						X			X			X	

Epoch	Open-Label Treatment ^{1,2,3}													
Visit	199	201	202	203	204	205	206	207	208	209	210	211	212	213

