9.5.2 Safety variables

Safety variables are:

- Adverse events
- Clinical laboratory values and vital signs
- Anti-AMG 334 antibodies

As safety analyses, patient incidence of treatment-emergent adverse events will be tabulated by system organ class and preferred term by treatment group for the Double-Blind Treatment Epoch.

Change from baseline for clinical laboratory values and vital signs will be summarized by visit and by treatment group for the double-blind treatment epoch.

The incidence and percentage of patients who develop anti-AMG 334 antibodies (binding and if positive, neutralizing) at any time will be tabulated by treatment group for the double-blind treatment epoch.

For the Open-Label Treatment Epoch, follow-up time adjusted patient incidence rate of treatment-emergent adverse events will be tabulated overall and by randomized treatment group. Measurements of safety laboratory and vital signs will be summarized over time and laboratory shift tables will be provided.

[figure not shown]
Safety analyses will be performed for the Double-Blind Treatment Epoch, as well as for the combined Open-Label Treatment Epoch and PTA-Open-Label Treatment Epoch.

[figure not shown]
[REDACTED]

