Study visit	Target Day	Study Day for vital signs, C-SSRS (for lab [REDACTED] include only Day1, Week 12, 24, 64)	Study Day [REDACTED]
Baseline	Please refer to Section 2.1.1		
Day 1	1	1	1
Week 4	29	16-43	16-43
Week 8	57	44-71	44-71
Week 12	85	1.72 to (week 12 OLTE dose date) for subjects who receive OLTE dose at week 12 2.72-99 for subjects who did not receive OLTE dose at week 12	1.72 to (week 12 OLTE dose date) for subjects who receive OLTE dose at week 12 2.72-99 for subjects who did not receive OLTE dose at week 12

For safety analyses which are summarized by study phase, analysis windows will be set up based on study phase:

Table 4 Study Phases for Safety analysis

Study Phase	Start Time Point	End Time Point
Double-blind Treatment Epoch	Study Day 1 (after the 1st DB IP Dose)	
 • First OLTE Dose Date - 1 for subjects receive OLTE IP dose; • MIN(EoS Date, last IP dose date + 84 days) for subjects did not receive any OLTE IP dose

Note: all anti-AMG 334 antibody data during all epochs will be included in immunogenicity analysis.

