2.2 Analysis sets

The **Randomized Analysis Set** (RAS) will consist of all participants who received a randomization number, regardless of receiving study medication.

The **Full Analysis Set** (FAS) will consist of all participants who started study medication and have completed at least one post-baseline monthly migraine day measurement in the doubleblind treatment epoch. In FAS, subjects will be analyzed according to randomized treatment, regardless of the actual treatment received. Analyses for efficacy endpoints and patient reported outcomes (PROs) will utilize this analysis set.

The **SAFety analysis set** (SAF) will consist of all randomized subjects who received at least one dose of investigational product and will be analyzed based on actual treatment received. Analyses for safety endpoints and summary of IP administration will utilize this analysis set. Rule of exclusion criteria of analysis sets is presented in [Appendix 5.5](#).

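### The immunogenicity sets are built on the efficacy FAS rather than the safety set, and the entire-study antibody table lists outdated visit numbers

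*SAP*

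**What the plan says.** Protocol 9.5.2 names "Anti-AMG 334 antibodies" among the safety variables, and immunogenicity is part of the safety objective in protocol Table 2-1. SAP 2.2 says of the SAF (randomized, at least one dose, actual treatment): "Analyses for safety endpoints and summary of IP administration will utilize this analysis set".

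SAP 2.7.6, within the safety chapter, starts from a different base: "The Immunogenicity prevalence set includes all patients in the Full analysis set with a determinant baseline IG sample", or at least one post-baseline sample. The incidence set is a subset of this and needs both samples. The FAS requires that patients "started study medication and have completed at least one post-baseline monthly migraine day measurement" in the double-blind epoch, and it keeps them in the randomized arm. The opening sentence of 2.7.6 instead tabulates double-blind antibodies for randomized subjects.

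For the whole trial, 2.7.6 counts antibodies developing at "any time post-dose (Visit 199, 203, 299, 301) will be tabulated by DBTE treatment group for the entire study". The note to SAP Table 4 says that "all anti-AMG 334 antibody data during all epochs will be included in immunogenicity analysis".

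**The concern.** Whether a dosed patient forms antibodies has nothing to do with completing a headache diary, so an efficacy condition should not decide who enters a safety summary. The patients it can remove are those who stopped early or stopped reporting, and a safety analysis should keep them. SAP 2.7.6 also gives no single denominator. Its first sentence and its two defined sets rest on different populations, so two programmers could report different rates for one endpoint.

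The visit list raises a separate problem. If a programmer treats it as a filter, the Week 64 sample is not used in the entire-study incidence. This matters most for patients randomized to placebo, who first receive AMG 334 at Week 12. Within protocol Table 6-2 their only later antibody samples are at Weeks 24 and 64.

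**Working it through.** The plan states no figure on this point, so the check compares the texts and then sizes the effect.

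**Population**

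1. Being in the SAF takes randomization and one dose (SAP 2.2).
2. Being in the FAS takes a dose and a post-baseline monthly migraine-day value. SAP 5.1.2 sets that value to missing when the interval has fewer than 14 eDiary days. SAP 5.5 confirms that patients without a post-baseline measurement of the primary endpoint leave the FAS.
3. The gap is therefore dosed patients with no evaluable diary month. They can still have antibody data: protocol Table 6-1 schedules samples at Week 12 or early discontinuation and at follow-up, and protocol 5.6.2 asks for both visits after a premature stop.
4. Size: the Amendment 3 rationale gives 246 randomized and 242 completing the double-blind epoch. 246 − 242 = 4, and 4/246 = 1.6%. Taking the non-completers as a rough guide (an assumption) gives 0 to 4 patients.
5. With 1:1 allocation an arm has about 246/2 = 123 patients. One patient is 1/123 = 0.8 percentage points; four in one arm would be 4/123 = 3.3%.
6. Antibody rates are not in the documents. Assumed rates near 2%, 5% and 10% illustrate the loss of one positive patient:
   - 2/123 = 1.6% becomes 1/122 = 0.8%
   - 6/123 = 4.9% becomes 5/122 = 4.1%
   - 12/123 = 9.8% becomes 11/122 = 9.0%
7. From the middle case, losing four positives gives 2/119 = 1.7%; losing four negatives gives 6/119 = 5.0%.

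**Arm**

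SAP 2.2 analyses the SAF by actual treatment. SAP 2.7 analyses it by randomized arm unless the wrong dose was received for the entire period. These two rules disagree. Under the second, FAS and SAF arms differ only for a patient mis-dosed throughout.

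**Visit list**

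1. The row "Anti-AMG Antibodies" in protocol Table 6-2 is marked in columns 1, 4 and 14: Visit 199 (Week 12), Visit 203 (Week 24) and Visit 213 (Week 64).
2. Visit 299 is Week 168 in Table 6-5, and protocol 5.6.1 counts a patient as having "completed the Open-Label Treatment Epoch when the patient has completed Visit 299 in the protocol".
3. The SAP introduction says it implements the March 2018 protocol, which is Amendment 3. That amendment's log records that Week 64 moved from Visit 299 to Visit 213. The SAP list (199, 203, 299, 301) fits the old numbering.
4. Samples at stake: 240 patients entered open label and 212 were ongoing when Amendment 3 was finalized. First screening was 20 March 2017. Adding at least 4 baseline weeks and 64 study weeks (68 weeks) gives 9 July 2018 at the earliest, after March 2018. Week 64 samples can thus come from at most 212 patients. Only someone positive at Week 64 and at no listed visit would be missed.

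**The case against.** The strongest reply is that almost nobody is affected and that other text protects the data. Much of this stands.

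- **Lost patients.** With 242 of 246 completing, few dosed patients can lack every diary month, and anyone never dosed is outside the SAF too. This stands and limits the size. It does not justify the diary condition.
- **Wrong arm.** A reader might infer that the FAS base puts antibody-positive patients in the wrong arm. The documents do not support this. No mis-dosing is recorded, and the arm rule in SAP 2.7 would leave a partly mis-dosed patient in the randomized arm even within the SAF. Tabulating open-label antibodies by original arm is a stated design choice.
- **Week 64.** A reader might infer that patients positive only at Week 64 will not be counted. That follows only if the parenthesis overrides the any-time wording around it and the Table 4 note. SAP 2.3.1 still defines study completion as 64 weeks and the SAP Table 3 header still ends at Week 64, so a missed renumbering is likelier than a decision to drop the sample. The by-timepoint prevalence summaries and the listing of positives carry no visit restriction. A listing, however, does not correct a reported incidence.
- **Scope.** Open-label analysis has its own SAP. True, but this SAP commits to an entire-study antibody table and names its visits.
- **Randomized subjects.** This may be loose wording, since SAP 2.7 describes the SAF in similar terms. It still leaves the denominator open.

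**Conclusion.** Two defects hold as written. The immunogenicity sets rest on the FAS, against the SAP's own assignment of safety endpoints to the SAF, and they carry a diary condition unrelated to antibody formation. The entire-study visit list is out of date; taken literally it omits Week 64 and conflicts with the rest of its own sentence and with the Table 4 note.

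The likely effect is small. About 0 to 4 of 246 patients could leave the antibody summaries, each worth about 0.8 percentage points of an arm. This rests on non-completers as a stand-in for missing diary months and on about 123 patients per arm. It is not a strict bound, because FAS and SAF counts are not given. A change of arm remains hypothetical. The visit list does not touch the double-blind results. Protocol Tables 6-3 and 6-4 are not in the text available, so later antibody visits could not be checked against the list.

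**What to change.** - In SAP 2.7.6, define the prevalence set as a subset of the SAF; the incidence set then follows. Use this population for every antibody table, in place of the reference to randomized subjects.
- Align the actual-treatment rule in SAP 2.2 and 2.7, stating how a patient given the wrong product at only some visits is handled. Moving the sets to the SAF does not settle this by itself.
- Replace the visit list with any post-dose antibody sample, which agrees with the Table 4 note, or add Visit 213 and check the remaining numbers against the full schedule.

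The cost is a few sentences in SAP 2.2, 2.7 and 2.7.6 and a change of population flag in the antibody programs. No new data are needed.

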2.7.6.1 Sample anti-drug antibody (ADA) status

Each ADA sample is assessed in a two tiered ADA testing approach. All ADA samples are analyzed in the initial screening assay (first tier). Samples testing positive in the screening assay are then subjected to a confirmatory assay to demonstrate that ADA are specific for AMG334 (second tier). Samples identified as positive in the confirmatory assay are considered ADA positive and are further characterized in the neutralization assay to indicate the presence of neutralizing antibodies (NAb).

The following properties of each sample will be provided in the source data:

- Positivity in confirmatory assay according to pre-specified confirmatory cut point: ADA positive (yes) or ADA negative (no)
- Presence of NAb: yes or no

Sample ADA status will only be listed. It is determined based on the following definitions:

- ADA-negative sample: Determinant sample where ADA screening or confirmatory assay is negative.
- ADA-positive NAb sample: Determinant sample where NAb ADA assay is positive.
- ADA-positive sample: Determinant sample where ADA confirmatory assay is positive.

The following definitions apply only to post-baseline ADA-positive samples with a corresponding determinant baseline sample:

- treatment-induced ADA-positive sample: ADA-positive sample post-baseline with ADA-negative sample at baseline.
- treatment-boosted ADA-positive sample: ADA-positive sample post-baseline with ADA-positive sample at baseline.

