5.6.5 Early study termination by the sponsor

The study can be terminated by Novartis at any time for any reason. This may include reasons related to the benefit-risk assessment of participating in the study, practical reasons, or for regulatory or medical reasons (including for example slow enrollment or an unreasonably low number of patients continuing). In the event that the study is terminated early, the IRBs/IECs will be informed. Should this be necessary, the patient must be seen as soon as possible and treated as a prematurely withdrawn patient. The investigator may be informed of additional procedures to be followed in order to ensure that adequate consideration is given to the protection of the patient's interests.

6 Visit schedule and assessments

Table 6-1, Table 6-2, Table 6-3 Table 6-4 and Table 6-5 list all of the assessments and indicate with an "X" when the visits are performed.

Patients must be seen for all visits on the designated day, or as close to it as possible. Missed or rescheduled visits should not lead to automatic discontinuation.

If the **COVID-19 pandemic** limits or prevents on-site study visits, alternative methods of providing continuing care may be implemented. Phone calls, virtual contacts (e.g. teleconsult) or visits by site staff to the patient's home depending on local regulations and capabilities, can replace on-site study visits, for the duration of the pandemic until it is safe for the patient to visit the site again (see Section 6.4 efficacy, Section 6.5.4 Laboratory evaluations, Section 6.5.6 Pregnancy and assessments of fertility, Section 6.6.6 AMG 334 Antibody testing, [REDACTED] Section 7 Safety monitoring and Section 7.6 Prospective suicidality assessment for further COVID-19 guidance related to sample collection).

Table 6-1 Assessment Schedule: Double-Blind Treatment

Epoch	Screen	Baseline ³	Double-Blind Treatment ^{1,4}				Follow-Up ²	Notes	
Visit	1	2	101	102	103	199	301	Follow up visit is 16 weeks after last dose of IMP (V103 / Wk 8), which is 12 weeks after last DBT visit (V199 / Wk 12).	
Week	-6	-4	Day 1	4	8	12/PSD/TD	24/FU		
Obtain Informed Consent	X								
Randomization			X						
Demography	X								
Medical & Medication History	X							Including prior prophylactic migraine medication	
Treatment Failure Confirmation	X								
Complete Physical Exam	S					S	S		
Brief Physical Exam		S	S	S	S				
Height	X								
Weight	X		X			X	X		
Vital Signs ⁵	X	X	X	X	X	X	X		
Chemistry/Hematology	X		X			X	X		

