2.7.6.2 Patient ADA status

The following overall summaries will be provided using the Immunogenicity incidence set:

- Treatment-boosted ADA-positive: number and percent of patients with at least one treatment-boosted ADA-positive sample. The denominator is the number of patients with an ADA-positive sample at baseline.
- Treatment-induced ADA-positive: number and percent of patients with at least one treatment-induced ADA-positive sample. The denominator is the number of patients with an ADA-negative sample at baseline.
- ADA-negative: number and percent of patients with no treatment-induced or treatment-boosted ADA-positive sample.

- ADA incidence (i.e. % ADA-positive): number and percent of patients with at least one treatment-induced or treatment-boosted ADA-positive sample.

The following summaries, both overall and by timepoint (including baseline), will be provided using the Immunogenicity prevalence set. For summaries by timepoint, the denominator is the number of patients at that timepoint with determinant samples:

- ADA prevalence: number and percent of patients with at least one ADA-positive sample.
- NAb ADA prevalence: number and percent of patients with at least one ADA-positive NAb sample.

A listing will be provided by subject with supporting information (i.e. ADA sample status at each timepoint (including positive samples) and patient ADA status

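### The SAP's ADA incidence row counts patients who were already antibody-positive at baseline, and its entire-study antibody table shows antibodies formed on open-label AMG 334 under placebo

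*SAP*

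**What the plan says.** SAP 2.7.6.1 calls a post-baseline positive sample treatment-induced if the baseline sample was negative. If the baseline sample was positive, it is a "treatment-boosted ADA-positive sample: ADA-positive sample post-baseline with ADA-positive sample at baseline". The sample properties listed for the source data are confirmatory positivity (yes/no) and neutralizing antibody (yes/no). Protocol 6.6.6 makes titre optional.

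SAP 2.7.6.2 gives induced and boosted rows with their own denominators (baseline-negative and baseline-positive patients). It then defines ADA incidence as the "number and percent of patients with at least one treatment-induced or treatment-boosted ADA-positive sample". The incidence set requires a determinant baseline sample and a determinant post-baseline sample; it does not exclude baseline-positive patients. No time window is stated for these summaries. The note to Table 4 in SAP 2.1.1 says that "all anti-AMG 334 antibody data during all epochs will be included in immunogenicity analysis".

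Protocol 9.5.2 asks for the patients "who develop anti-AMG 334 antibodies (binding and if positive, neutralizing) at any time will be tabulated by treatment group for the double-blind treatment epoch". SAP 2.7.6 plans such a table, which "will be tabulated by treatment group for randomized subjects during DBTE". It adds a second one, of patients who develop antibodies "at any time post-dose (Visit 199, 203, 299, 301) will be tabulated by DBTE treatment group for the entire study".

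**The concern.** Incidence should count antibodies that appear after treatment starts. Under the SAP rule, a placebo patient with pre-existing antibody who simply stays positive is labelled treatment-boosted and counted as incident, without ever receiving AMG 334. The yes/no properties listed cannot show whether anything rose.

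In the entire-study table, Visits 203 and 299 fall in the open-label epoch, when everyone who entered receives AMG 334 140 mg (Protocol 3.3). A patient randomized to placebo who forms antibodies there is counted in the placebo column, together with samples taken on placebo. That column cannot be read as an unexposed background rate.

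Anti-drug antibody evaluation is one of the two endpoints named for the safety objective (Protocol Table 2-1), so the labels on these rows matter even though nothing is tested.

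**Working it through.** The plan states no antibody rate, so there is no figure to reproduce. The rates below are assumptions.

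**1. The incidence row.** Let b be the share of an arm positive at baseline and still positive later, and r the induced rate among baseline-negative patients. I take the incidence set as denominator.

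- Row as defined = b + (1 − b)r
- Share of the row that is baseline-positive = b / (b + (1 − b)r)
- Between-arm difference, with r = 0 on placebo = (1 − b)r

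With r = 5% on AMG 334 and 0% on placebo:

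| b | AMG 334 row | Placebo row | Baseline-positive share of AMG 334 row | Difference |
|---|---|---|---|---|
| 0% | 5.00% | 0% | 0% | 5.00 points |
| 1% | 5.95% | 1% | 16.8% | 4.95 points |
| 2% | 6.90% | 2% | 29.0% | 4.90 points |
| 5% | 9.75% | 5% | 51.3% | 4.75 points |

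The level rises in both arms. The difference falls by at most 0.25 points.

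In counts, assume 123 per arm, 4 persistent baseline positives in each, 6 new positives on AMG 334 and none on placebo. The row reads 10/123 = 8.1% v 4/123 = 3.3%. The induced row reads 6/119 = 5.0% v 0/119 = 0%.

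**2. The entire-study table.** Protocol Amendment 3 reports 246 randomized and 240 entering open label, so 246 − 240 = 6 did not. With 1:1 allocation I assume 246/2 = 123 per arm. Between 123 − 6 = 117 and 123 placebo patients then received AMG 334. If r is their induced rate on drug and none turned positive on placebo, the placebo column gains 117r to 123r patients:

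- r = 1%: 1.2 patients, 0.95–1.0% of 123
- r = 5%: 5.9–6.2 patients, 4.8–5.0%
- r = 10%: 11.7–12.3 patients, 9.5–10%

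Not every Visit 301 sample is affected. Protocol Table 6-1 notes "Follow up visit is 16 weeks after last dose of IMP"; for a placebo patient who never entered open label, that sample belongs under placebo.

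**3. The visit list.** Protocol Table 6-2 takes antibody samples at Visits 199, 203 and 213, the last at Week 64. Protocol 5.6.1 makes Visit 299 the end of the open-label epoch, and Table 6-5 places it at Week 168. The SAP table lists 199, 203, 299 and 301. Read literally, it omits the Week 64 sample.

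**4. The window.** For patients with no open-label dose, SAP Table 4 ends the double-blind safety phase at the earlier of end of study and last dose + 84 days. Visit 301 falls 16 × 7 = 112 days after the last dose. The all-epochs note does not say which rule governs the by-arm summaries in SAP 2.7.6.2.

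**The case against.** The SAP glosses the incidence row as percent ADA-positive and shows both components separately with suitable denominators. This stands: the induced row fully recovers new antibodies, provided its window is stated. A reader might infer that the SAP departs from the protocol's request for patients who develop antibodies. It does not: the table in SAP 2.7.6 limited to the double-blind epoch carries that out, and the incidence row is additional.

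The entire-study table is supplementary and openly labelled by original arm. The protocol does something similar for open-label events, where "treatment-emergent adverse events will be tabulated overall and by randomized treatment group". That display is confined to the open-label epoch, however, whereas this table puts placebo-period and drug-period samples in one column. Prevalence by timepoint, shown by arm under the general rule in SAP 2.1, and the by-subject listing let a reader separate the periods. These limit the harm but do not correct the table.

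SAP 1 leaves the open-label analysis to a separate plan, which may handle former-placebo patients differently. That cannot be judged here, and SAP 2.7.6 still specifies the table.

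The rates are assumed. Exclusion criterion 23 bars prior exposure to investigational CGRP-pathway products, and nothing in the documents supports baseline positivity as high as 5%. That stands too.

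**Conclusion.** The point holds as a minor one. The incidence row is misdefined and mislabelled, the entire-study table attributes some drug-period antibodies to placebo, and that table's visit list misses Week 64.

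A reader might go further and infer that the randomized antibody comparison is contaminated, or that the rate of new antibodies is lost. The documents support neither. The double-blind table is sound if kept to double-blind samples, and the induced row is planned. Nor do they show that open-label samples will enter the SAP 2.7.6.2 summaries; the window is simply unstated.

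Size depends entirely on assumed rates. The first fault has no effect if baseline positivity is 0%; the second has none if former-placebo patients form no antibodies on drug. All these outputs are descriptive (SAP 2.7 plans no safety testing), so no test, alpha or efficacy result changes.

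**What to change.** - Report the planned treatment-induced rate among baseline-negative patients as ADA incidence.
- Relabel baseline-positive patients who remain positive as persistently positive. Use boosted only with a pre-specified titre rise, if titre is available.
- In the entire-study table, give former-placebo patients who received AMG 334 a separate column. Count only samples after their first AMG 334 dose, with the last sample before that dose (Visit 199 where available) as baseline.
- Keep their samples up to and including the pre-dose Visit 199 sample under placebo, along with the Visit 301 samples of placebo patients who did not enter open label.
- Restrict the by-arm summaries in SAP 2.7.6.2 to samples before the first open-label dose. For non-entrants, state whether Visit 301 (112 days after the last dose) is included, and reconcile this with the 84-day limit and the all-epochs note in Table 4.
- Add Visit 213 to the visit list.

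The cost is SAP wording and reprogramming of one descriptive table set, with one extra column. No new data are needed unless a titre rise is used.
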